8.4.2.2 Day 2(24 ± 4] hours)

On Day 2 (24 ± 4] hours):

- The subject will self-assess HAE pain using diary FPS-R
- Injection site reaction will be recorded
- Concomitant medications will be recorded
- Adverse events will be recorded

8.4.3 Follow-up Visits

Each treatment for a subsequent attack will require a Day 8 and a Day 90 follow up visit. If a subsequent attack occurs within 3 days of the Day 8 follow-up visit for the previous attack the visits for Day 1 (of the subsequent icatibant-treated attack) and Day 8 (of the prior icatibant-treated attack) will be combined. If a subsequent attack occurs within 7 days of the Day 90 follow-up visit for the previous attack the visits for Day 8 (of the subsequent icatibant-treated attack) and Day 90 (of the prior icatibant-treated attack) will be combined

8.4.3.1 Day 8 (± 1 day)

The subject will return to the hospital/study on Day 8 (± 1 day) The following evaluations and sample collections will be performed on Day 8:

- Vital signs
- Reproductive hormone assessments
- Immunogenicity evaluation
- Injection site reaction evaluation
- Concomitant medications will be recorded
- Adverse events will be recorded

8.6.2 Follow-up Visit 8.4.3.2 Day 90 ± 7 days

- \blacktriangleleft Physical examination
- \blacktriangleleft Vital signs
- \blacktriangleleft Height and weight
- \blacktriangleleft Clinical laboratory tests (serum chemistry, hematology, and urinalysis)
- \blacktriangleleft Urine pregnancy test (in females of childbearing potential)
- \blacktriangleleft Reproductive hormone assessments
- \blacktriangleleft Immunogenicity evaluation
- \blacktriangleleft Menstrual cycle history (in pubertal/postpubertal females)
- \blacktriangleleft Recording of concomitant medications
- \blacktriangleleft Assessment of adverse events
- \blacktriangleleft Documentation of HAE attack(s) not treated with icatibant

8.6.3 Telephone Contact (Month 6 ± 7 days)

The scheduled telephone contact will document pubertal changes/milestones, if any-

- \blacktriangleleft Pubareche
- \blacktriangleleft Menarche (females only)

- ~~Changes in menstrual cycle (females only)~~
- ~~Pregnancy (females and male partner)~~

Section impacted by change: Section 10.7, Efficacy Analyses

Revised Text:

Efficacy analyses will be performed on the Efficacy Population. The primary efficacy endpoint is the time to onset of symptom relief measured using the investigator-reported symptom score. **For the initial icatibant-treated attack**, the investigator will report symptom scores at pretreatment and 1, 2, 4, and 6 hours post treatment, and at 8 hours post treatment for subjects who had not shown complete resolution of HAE symptoms at 6 hours. **For subsequent icatibant-treated attacks the investigator will report symptom scores at pretreatment and 1 and 2 hours post treatment, and every 2 hours afterwards until discharge.** Eight symptoms will be assessed for abdominal and cutaneous attacks, and 13 symptoms will be assessed for laryngeal attacks. Time to onset of symptom relief is defined as the earliest time post treatment at which there is a 20% improvement in the average post-treatment symptom score with no worsening of any single component score. The median time and the 95% confidence interval will be calculated using the Kaplan-Meier methodology.

A tabular summary of the average investigator-reported symptom score and the change from baseline in the average investigator-reported symptom score will be presented by the stratification group and the icatibant-treated-attack **exposure** number. An alternative analysis will focus on the time to minimal symptoms and is defined as the time from study drug administration to the earliest time post treatment when all symptoms are either absent or mild. The median time and 95% confidence interval will be calculated using Kaplan-Meier methodology.

Added text:

Home healthcare provider or parent/legal guardian/caregiver symptom scores (referred to as caregiver-reported symptom scores hereafter) will be measured for all subjects' subsequent icatibant-treated attacks. A tabular summary of the average caregiver-reported symptom scores and the change from baseline in the average caregiver-reported symptom scores will be presented by the stratification group and the subsequent icatibant treated attack number. For individual caregiver-reported symptom scores, a shift table from baseline will be presented for each post-treatment time point.

Section impacted by change: Section 10.8, Other Analyses

Revised Text:

The number and percentage of subjects who received rescue medications before the onset of symptom relief will be summarized by the stratification group and icatibant-treated-attack **exposure** number.

Section impacted by change: Section 10.9, Data Monitoring and Interim Analysis

Revised Text:

Based on the anticipated sequence of data being generated in the study, an initial interim analysis of the data from ~~pubertal/postpubertal patients~~ **the initial attack** (N=20**30**) is planned. It is expected that this will be followed by ~~an interim analysis of data from prepubertal patients (N=10), and then~~ by a final analysis to include the data of patients treated for subsequent attacks. This sequence is based on the anticipated sequence of data being generated during the study and may be modified to fit the actual study conduct.

Section impacted by change: Section 11.12, Data Generation and Analysis

Revised Text:

Concomitant medication will be coded using the World Health Organization Drug Dictionary (WHO-DD) (2004, Q4 December 2011).

Section impacted by change: Section 11.14, Financial Disclosure

Revised Text:

The investigator should disclose any financial interests in the sponsor as described in 21 CFR Part 54 prior to beginning this study. The appropriate form will be provided to the investigator by the sponsor, which will be signed and dated by the investigator, prior to the start of the study, ~~at the end of the study, and one year post study (or site) closure.~~ Changes in status concerning financial interests during the study and for 1 year after its completion will must be disclosed by the Investigator in accordance with 21 CFR Part 54.

Section impacted by change: [Appendix 1](#), [Appendix 2](#), and [Appendix 3](#)

Updated to reflect the changes to the protocol.

Section impacted by change: [Appendix 4](#)

Revised text:

~~Pubic hair development reflects adrenal function.~~ **DO NOT use development of pubertal hair as evidence of progression to Tanner stage II because this could reflect increased adrenal gland function (adrenarche) in prepubertal subjects and** not hypothalamic/gonadal function. The descriptions used in this table are intended to provide guidance for the investigators and may not align with descriptions of pubic hair and pubertal stage in other sources.

Section impacted by change: [Appendix 7](#)

Updated to reflect the change in Medical Monitor

## 1. LIST OF ABBREVIATIONS AND DEFINITIONS

### 1.1 Abbreviations

AE	Adverse Event
BMI	Body Mass Index
C1-INH	C1 inhibitor
CRF	Case Report Form
ECG	Electrocardiogram
FLACC	Faces, Legs, Activity, Cry, and Consolability
FPS-R	Faces Pain Scale – Revised
HAE	Hereditary Angioedema
ITT	Intent To Treat
IV	Intravenous
LOCF	Last Observation Carried Forward
MedDRA	Medical Dictionary for Regulatory Activities
PD	Protocol Deviation
PK	Pharmacokinetic
SAE	Serious Adverse Event
SAP	Statistical Analysis Plan
SC	Subcutaneous
SOC	System Organ Class
SOP	Standard Operating Procedure
WHO	World Health Organization
WHO-DD	World Health Organization-Drug Dictionary

## 2. INTRODUCTION

### 2.1 Purpose of the Statistical Analysis Plan

This statistical analysis plan (SAP) provides a technical and detailed elaboration of the planned statistical analyses on safety and efficacy endpoints for protocol HGT-FIR-086, a multicenter, open-label, non-randomized study to assess the pharmacokinetics (PK), tolerability, and safety of a single subcutaneous (SC) administration of icatibant in children and adolescents with hereditary angioedema. SAP for PK endpoints will be provided in a separate document.

This study evaluated the effect of a single administration of icatibant in children and adolescents with hereditary angioedema (HAE). It also examined the effect of repeated exposures of icatibant in adolescents. This SAP presents the statistical analysis methods on complete safety and efficacy results for single administration of icatibant in at least 10 prepubertal children and at least 20 adolescents with HAE treated once with icatibant and repeated exposure of icatibant during subsequent HAE attacks in adolescents.

### 2.2 Background

This is an open-label, non-randomized, single-arm study to evaluate the PK, tolerability, safety including reproductive hormone assessments, and efficacy of a single SC administration of icatibant in approximately 30 pediatric subjects with HAE during an initial acute attack. Details of the study design, rationale, and procedures are documented in [Protocol HGT-FIR-086](#).

### 2.3 Study Rationale

Three controlled Phase III studies established the safety and efficacy of icatibant as a treatment for acute attacks of HAE. Icatibant has not been evaluated in clinical trial subjects below the age of 18 years. This study was designed to evaluate the PK, tolerability, safety including reproductive hormone assessments, and efficacy of a single SC administration of icatibant in subjects from 2 to less than 18 years of age.

### **3. STUDY OBJECTIVES**

The study objectives are listed below.

#### **3.1 Objectives**

The objectives of this study are:

- To investigate the PK, tolerability, and safety of a single SC dose of icatibant in children and adolescents with HAE.
- To evaluate the efficacy of a single SC dose of icatibant in children and adolescents with HAE.
- To evaluate the effect on reproductive hormone levels after a single SC dose of icatibant in children and adolescents with HAE.

#### **3.2 Other Objectives**

Other objectives of this study are:

- To evaluate the continued safety of icatibant in pubertal/postpubertal children after repeated exposures.
- To evaluate the efficacy of icatibant in the treatment of acute HAE attacks in pubertal/postpubertal children after repeated exposures.
- To evaluate the effect on reproductive hormone levels in pubertal/postpubertal children after repeated exposures.

## 4. STUDY DESIGN

### 4.1 General Description

This is an open-label, non-randomized, single-arm study to evaluate the PK, tolerability, and safety, including effects on reproductive hormones, of a single SC administration of icatibant in pediatric subjects with HAE.

The study enrolled children and adolescents from 2 to less than 18 years of age, divided into 2 groups: prepubertal (Tanner stage I) and pubertal/postpubertal (Tanner stages II to V).

After a qualifying screening period, the PK, safety/tolerability, and efficacy of treatment with SC icatibant was evaluated in at least 20 subjects (10 prepubertal and 10 pubertal/postpubertal subjects) who presented with cutaneous, abdominal, or laryngeal symptoms of an acute attack of HAE.

The PK and safety/tolerability of SC icatibant was evaluated in at least 10 additional pubertal/postpubertal subjects who met screening criteria, but received treatment with SC icatibant in the absence of a current acute HAE attack.

Subjects will receive treatment with a single SC administration of icatibant on Day 1 and will be monitored closely in the hospital/study center for at least 6 to 8 hours after treatment. Subjects will undergo PK and safety assessments; efficacy assessments will be performed if treatment occurs during an acute HAE attack. All subjects will have serum reproductive hormone measurements.

A subject may be discharged after completion of assessments at 6 hours post treatment, if deemed medically stable in the investigator's clinical judgment and, if applicable, the subject's HAE symptoms have resolved (the subject's investigator-rated symptom score must be zero, denoting the absence of symptoms). If HAE symptoms have not completely resolved at 6 hours (ie, the investigator-rated symptom score is >0), the subject shall remain in the hospital/study center for at least 8 hours after icatibant administration for further evaluation. Telephone follow-up will occur at both 24 and 48 hours after treatment. Subjects will return to the hospital/study center for scheduled assessments on Day 8 and for a follow-up visit on Day 90.

A table showing the Schedule of Events for the study is provided in [Appendix III: Schedule of Events](#).

### 4.2 Discussion of Study Design

This study has an open-label, single arm design.

The study is intended to determine the PK profile of SC icatibant when administered to children and adolescents with HAE and to identify an optimal pediatric dosing regimen.

In addition, the study is intended to establish the tolerability and safety of icatibant in children and adolescents, particularly with respect to potential effects on reproductive development, and to demonstrate the effectiveness of icatibant in relieving the symptoms of acute HAE attacks. Therefore, this study will help determine whether icatibant can address an unmet medical need for a safe and effective treatment for acute attacks of HAE in pediatric patients.

#### 4.3 **Method of Assigning Subjects to Treatment Group**

Not applicable to this single arm study.

#### 4.4 **Blinding**

Not applicable to this open-label study.

#### 4.5 **Determination of Sample Size**

The study will enroll a sufficient number of children and adolescents to ensure study completion of 30 evaluable subjects. The study population is planned to consist of at least 10 prepubertal and 20 pubertal/postpubertal subjects from 2 to less than 18 years of age. Though empirically derived and not based on a formal sample size calculation, this sample size will provide basic information concerning the PK, tolerability and safety, and efficacy of icatibant in children and adolescents with HAE.

## 5. STUDY ENDPOINTS

The primary endpoints of this study are:

- The PK profile of icatibant after a single SC injection in pediatric subjects (in prepubertal children with an acute attack of HAE and pubertal/postpubertal children with or without an acute attack of HAE).
- The tolerability and safety of SC icatibant as assessed by injection site reactions, adverse events, vital signs, ECG recordings, physical examination, clinical laboratory parameters (serum chemistry [including liver function tests], hematology, urinalysis), reproductive hormone levels, and immunogenicity (presence of anti-icatibant antibodies).

The secondary endpoints (only for subjects treated with icatibant during a HAE attack) of this study are:

Time to onset of relief of symptoms and time to minimal symptoms, as measured by investigator- and subject-reported outcomes

- For all subjects (2 to <18 years of age): investigator assessment and scoring of cutaneous, abdominal, and laryngeal symptoms of acute HAE attacks by an investigator-rated symptom score.
  - The time to onset of relief of symptoms, defined as the earliest time at which a 20% improvement is seen in the average post-treatment score with no worsening of any single component score.
  - The time to minimal symptoms, defined as the earliest time post-treatment when all symptoms are either mild or absent based on the investigator-rated symptom score.
- For subjects  $\geq 4$  years of age only: subject self-assessment of HAE-related pain using the Faces Pain Scale-Revised (FPS-R).
  - The time to onset of relief of symptoms, defined as the earliest time at which the post-treatment score improves by at least one level.
  - The time to minimal symptoms, defined as the earliest time at which the post-treatment score improves to zero (or no pain).
- For subjects <4 years of age only: investigator assessment of HAE-related pain (cutaneous, abdominal, and laryngeal) using a validated pain scale (Faces, Legs, Activity, Cry, and Consolability [FLACC]).
  - The time to onset of relief of symptoms, defined as the earliest time at which a 20% improvement is seen in the total post-treatment score.
  - The time to minimal symptoms, defined as the earliest time at which the total post-treatment score improves to zero.
- Incidence of rescue medication use.

- Proportion of subjects with worsened intensity of clinical HAE symptoms between 2 and 4 hours after treatment with icatibant.

## 6. EFFICACY AND SAFETY VARIABLES

### 6.1 Schedule of Evaluations

Please refer to [Appendix III: Schedule of Events](#) for details of assessments performed at each visit.

### 6.2 Safety Assessments

The safety and tolerability parameters include AEs, vital signs, ECG, local tolerability at the injection site, reproductive hormone levels, immunogenicity, and standard hematology, serum chemistry, and urinalysis.

### 6.3 Efficacy Assessments

#### 6.3.1 Investigator Symptom Score

The investigator will use a symptom score to assess the severity of symptoms of acute cutaneous, abdominal, and laryngeal attacks of HAE using the following 5-point scale.

0 = none; absence of symptoms

1 = mild (no to mild interference with daily activities)

2 = moderate (moderate interference with daily activities)

3 = severe (severe interference with daily activities)

4 = very severe (very severe interference with daily activities)

For attacks classified as cutaneous and/or abdominal, investigator-rated symptom scores will be collected for 8 symptoms: abdominal tenderness, nausea, vomiting, diarrhea, skin pain, erythema, skin irritation, and skin swelling.

For attacks classified as laryngeal, investigator-assessed symptom scores will be collected for 13 symptoms: abdominal tenderness, nausea, vomiting, diarrhea, skin pain, erythema, skin irritation, skin swelling, dysphagia, voice change, breathing difficulties, stridor, and asphyxia.

#### 6.3.2 FPS-R

The Faces Pain Scale – Revised (FPS-R) is a self-reported measure used to assess the intensity of children's pain and it is scored using a 0 to 10 scale ('0'='no pain' and '10'='very much pain'). Subjects who are at least 4 years of age will self-assess HAE-related pain using the FPS-R.

#### 6.3.3 FLACC

Subjects who are below 4 years of age will undergo investigator assessment of HAE-related symptoms using the Faces, Legs, Activity, Cry, and Consolability (FLACC) compartmental

pain scale. The FLACC is a behavior pain assessment scale for use in preverbal children or children with limited verbal capability who are unable to provide reports of pain. Each of the five categories (F) Face; (L) Legs; (A) Activity; (C) Cry; (C) Consolability is scored from 0-2, which results in a total score between zero and ten.

## 7. STATISTICAL ANALYSES

### 7.1 General Considerations

All statistical analyses will be performed using SAS® statistical software (SAS Institute, North Carolina, USA) except for the population PK modeling which will be performed with nonlinear mixed effect modeling software (eg, Phoenix NLME module, Pharsight Corp.). A separate analytic plan will be developed to support the analysis of PK data. The analysis methods for all other study data (demographic and pretreatment characteristics, efficacy variables, and safety variables) will be detailed in the SAP.

Data will be summarized with respect to disposition, demographic, pre-treatment characteristics, safety variables, and efficacy variables. Summary statistics for continuous variables will include the number of subjects, the mean, median, standard deviation, and range. For categorical data, summaries will include counts and percentages. Time-to-event data will be summarized using Kaplan-Meier estimates of the 25th, 50th (median), and 75th percentiles with associated 2-sided 95% confidence intervals, as well as percentage of censored observations. Plots of the Kaplan-Meier curves and supporting data listings detailing each subject's contribution to the analysis will be provided.

### 7.2 Analysis Populations

The following populations will be used in the analysis:

- The Efficacy Population will consist of those subjects who were treated with icatibant for their first and any additional attacks during the study.
- The Safety Population will consist of those subjects who were treated with icatibant at least once during the study (irrespective of the presence of an HAE attack).

All efficacy analyses will be performed on the Efficacy Population. The corresponding tabular summaries will be presented by the icatibant exposure number. For the initial icatibant exposure, the analyses will be presented by the pubertal status (Pre-pubertal vs. Pubertal/Post-pubertal) and overall; for the subsequent icatibant exposures, the analyses will be presented by the administration type (Study Site Personnel (HCP Administration) vs. Home Healthcare Providers/Patient/Parent/Legal Guardian/Caregiver (Caregiver Administration)) and overall.

Safety and tolerability analyses will be based on the Safety Population. All tabular summaries within this population will be presented by the icatibant exposure number. For the initial icatibant exposure, the analyses will be presented by the pubertal status (Pre-pubertal vs. Pubertal/Post-pubertal) and overall; for the subsequent icatibant exposures, the analyses will be presented by the administration type (HCP Administration vs. Caregiver Administration) and overall.

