4.1.3.2 Subsequent Icatibant-Treated Attacks

Subsequent treatment with icatibant may be offered to pubertal/postpubertal subjects who have received initial treatment and who present subsequently with an attack at least 3 days after prior treatment. Subjects will be eligible for treatment with icatibant until a total number of at least 10 adolescents have been treated 3 times with icatibant.

For all subjects who remain enrolled in the study for longer than 6 months, a study visit will be scheduled every 6 months to collect baseline information and to conduct training for parents/legal guardian/caretakers for subjects who have expressed an interest in receiving icatibant at home. In addition, for all subjects who remain enrolled in the study a safety telephone contact will be scheduled every month to collect information concerning AEs, weight, eligibility, and HAE attacks not treated within the study.

When a pubertal/postpubertal subject experiences an acute HAE attack, subjects (parent/legal guardian/caregiver) will contact the hospital/study center (or their home healthcare professional in the event the investigator is not available) to confirm the HAE attack diagnosis.

The investigator (or the home healthcare professional in the event the investigator is not available), in consultation with the subject's preference, will determine whether the subject will be treated at the hospital/study center, at home by a qualified home healthcare personnel, or at home by the trained parent/legal guardian/caregiver. The qualified home healthcare person will be contacted, if applicable.

For subsequent attacks, study drug may be administered by study site personnel at the hospital/study center or by qualified home healthcare personnel at the subject's home. Alternatively, a parent/legal guardian/caregiver will be allowed to administer or the subject (under the supervision of a parent/legal guardian/caregiver) will be allowed to self-administer the investigational product after having received appropriate training. For all subsequent laryngeal attacks, subjects should be advised to seek medical attention in an appropriate healthcare facility immediately following treatment with icatibant.

Except for PK determinations, all primary and secondary endpoints are to be measured after each administration. Safety, reproductive hormones, and other assessments in association with

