6.2 Treatment Administered

All subjects will receive treatment with icatibant as a single, weight-adjusted dose of 0.4 mg/kg up to a maximum of 30 mg administered in the abdominal region as a SC injection.

Pubertal/postpubertal subjects are potentially eligible to receive an initial treatment with icatibant (in the presence or the absence of an attack) and to receive 2 additional treatments with icatibant for an attack of acute HAE. Thus, a maximum of 3 doses of icatibant may be administered to a pubertal/postpubertal subject in the study, while all prepubertal subjects will receive a single dose of icatibant.

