### 7.9.7 Reproductive Hormone Assessments

Reproductive hormone levels will be measured in all subjects at pre-treatment, and 6 hours, 8 days and 90 days post-treatment for the initial icatibant treatment, and pretreatment, 8 days and 90 days post-treatment for subsequent icatibant-treated attacks. FSH, LH, estradiol, and progesterone will be summarized for females, and FSH, LH, and testosterone will be summarized for males. Observed values and changes from pre-treatment will be summarized by study time-point. The number and percentage of subjects with levels outside the normal range defined for their sex and pubertal status will be summarized by study time-point. Observations below the limit of detection will be considered abnormal if the lower limit of normal is not zero.

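### Repeat-exposure results are tabulated by exposure number on partly overlapping sets of subjects, with no same-subject summary, so change with repeated use is mixed with who was retreated

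*SAP*

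**What the plan says.** SAP 3.2 lists three further objectives, all on repeated use in adolescents: safety, efficacy, and "To evaluate the effect on reproductive hormone levels in pubertal/postpubertal children after repeated exposures".

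For efficacy tables SAP 7.2 states: "The corresponding tabular summaries will be presented by the icatibant exposure number". Safety follows the same rule, and 7.8 and 7.9 repeat it. Exposure 1 is split by pubertal status. Exposures 2 and 3 are split by who gave the injection. The shells in SAP Appendix I match, with one table for exposure 1 and another for exposures 2 and 3. SAP 9.1, 9.6 and 9.7 plan no modelling, subgroup or sensitivity analysis.

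On who is retreated, Protocol 4.1.3.2 keeps treatment open "until a total number of at least 10 adolescents have been treated 3 times with icatibant", while under Protocol 6.2 "all prepubertal subjects will receive a single dose of icatibant". Protocol 4.1.3.1 omits efficacy assessment when the first dose is given without an attack. Protocol 4.1.2 counts such a subject's first treated attack as the second exposure for safety purposes.

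Protocol 10.3 groups efficacy by treated-attack number, and SAP 8.2 reports no change from the protocol's analyses.

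For hormones, SAP 7.9.7 plans a pretreatment, Day 8 and Day 90 sample around later attacks and says: "Observed values and changes from pre-treatment will be summarized by study time-point". Protocol 8.4.1 allows the later baseline to be taken up to 6 months before treatment. Only immunogenicity has an explicit rule for which baseline applies (SAP 10.2.13).

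**The concern.** A reader will compare the exposure 1, 2 and 3 tables to judge whether the drug works and is tolerated equally well on repeat use. Those tables do not hold the same subjects. Exposure 3 holds only adolescents who had further attacks, stayed in the study and were retreated. If they differ from the others in attack pattern, response or tolerability, the tables change even when no individual does.

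Efficacy has a second layer. For an adolescent first dosed without an attack, exposure 2 is the first treated attack; for one first dosed during an attack, it is the second. With at most three doses, exposure 3 likewise mixes second and third treated attacks.

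For hormones the question is whether anything builds up over doses. The later pretreatment sample is normally drawn after dose 1. If it is the reference for later change, that change cannot show what dose 1 left behind. The protocol's own nonclinical background (1.2.3) makes this a question worth answering directly.

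**Working it through.** **The plan's own figure.** The sample size is "Though empirically derived and not based on a formal sample size calculation", with "at least 10 prepubertal and 20 pubertal/postpubertal subjects". Only the sum can be checked: 10 + 20 = 30. No power or precision figure is given.

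**Step 1. Search for a same-subject output.** SAP 7.2 to 7.9, 9.1 to 9.7, 10.2 and the table, figure and listing shells contain no summary that restricts exposure 1 to subjects treated again, pairs a subject's exposures, or gives hormone change from the first pre-dose value for later exposures. Across exposures there are only by-subject listings and pooled summaries by pubertal status (for example AEs and immunogenicity), which combine exposures without comparing them.

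**Step 2. Who is in each set, at the minimum counts.**
- Safety: exposure 1 has 30 subjects (10 prepubertal, 20 adolescents). Exposure 3 has as few as 10, all adolescents and all contained in exposure 1.
- Efficacy: exposure 1 has 20 subjects (10 prepubertal, 10 adolescents). The other 10 adolescents first contribute at exposure 2. The 10 thrice-treated subjects can therefore overlap the 10 adolescents with exposure-1 efficacy data by anything from 0 to 10. If they were a random 10 of the 20 (assumption), the mean overlap is 10 × 10/20 = 5, and the hypergeometric probability of 3 to 7 is 0.98.

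**Step 3. False change for a safety outcome.** Let m of N subjects return, with mean R in returners, O in the others, and d = R − O. With no change in anyone:

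later − first = R − [(m/N)R + (1 − m/N)O] = d × (1 − m/N)

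| Reference at exposure 1 | m/N | 1 − m/N | d = 0.25, 0.5, 1.0 SD gives |
|---|---|---|---|
| 20 adolescents | 10/20 | 0.50 | 0.125, 0.25, 0.50 SD |
| 20 adolescents | 15/20 | 0.25 | 0.06, 0.125, 0.25 SD |
| All 30 | 10/30 | 0.67 | 0.17, 0.33, 0.67 SD |

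It is zero only if d is zero or everyone in the reference group returns. The values of d are assumptions.

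**Step 4. False change for 1-hour relief.** Assume 80% relief in the thrice-treated at every attack and 50% in the other adolescents. Let k be the overlap in Step 2. The exposure-1 adolescent rate is [80k + 50(10 − k)]/10, and exposure 3 shows 80%, so:

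false gain = 30 × (1 − k/10) points

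This is 0 at k = 10, 15 at k = 5 (65% against 80%), and 30 at k = 0. Assumed rates of 70/60 give 0 to 10 points; 90/40 gives 0 to 50.

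**Step 5. Hormones.** Suppose each dose shifts a hormone by s, and a fraction f of each earlier dose's shift persists (both assumed). After dose 3, change from the first pre-dose value is s(1 + 2f). Change from a baseline drawn after dose 2 is s. If one six-monthly baseline drawn between doses 1 and 2 serves both later exposures, it is s(1 + f). At f = 0.5 these are 2s, s and 1.5s; at f = 1 they are 3s, s and 2s. At f = 0 all three equal s.

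**Step 6. Precision of a same-subject comparison.** In 10 subjects with within-subject correlation ρ (assumed), the standard error in SD units is √(2(1 − ρ)/10): 0.37, 0.32, 0.24 and 0.14 at ρ = 0.3, 0.5, 0.7 and 0.9. The composition term of Step 3 is zero.

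**The case against.** The strongest reply is that the study is descriptive, plans no test between exposures, and already gives a careful reader much of what is needed. Demographics and HAE history, including recent attack frequency, are shown by exposure number (SAP 7.4, 7.5). All efficacy and safety results are listed by subject (7.8, 7.9). The adolescent column at exposure 1 can be set against the overall column later, since only adolescents are retreated. This stands in part: the different column splits do not by themselves block comparison. But the adolescent column still includes non-returners, demographics do not show outcomes in the same people, and a listing is not a planned summary.

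Several stronger readings are tempting but unsupported.
- A reader might infer that each exposure involves different people. For safety the later sets are nested in the first; only for efficacy could exposures 1 and 3 be disjoint.
- A reader might infer that a lasting hormone effect is hidden. The exposure-1 table shows change to Day 90, on a date kept even if another attack intervenes (Protocol 8.3.3). Observed values and out-of-range counts at later exposures do not depend on a baseline. A per-exposure hormone baseline is itself an inference.
- A reader might infer that good responders are over-represented. Retreatment requires a new attack, not a prior response, so this is possible but not shown.
- A reader might infer that the SAP simply departs from the protocol. Protocol 10.3 uses treated-attack number for efficacy, but Protocol 10.7 and 10.8 use exposure number for the average symptom score and rescue medication. The protocol is not uniform.

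**Conclusion.** The point holds as a cheap improvement. The planned tables mix any effect of repeated use with who was retreated, and no planned summary separates the two, although repeated exposure is the subject of three objectives.

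For safety outcomes the distortion is half the returner difference when 10 of 20 adolescents receive three doses. For 1-hour relief it is 0 to 30 points at assumed rates of 80% and 50%. These sizes rest on the minimum counts and on assumed differences, so they show what could happen, not what did. A 1-hour relief calculation using all 20 adolescents at exposure 1 would be wrong, because about 10 of them have no efficacy data there.

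The efficacy numbering is also unsettled: SAP 7.2 and Protocol 10.3 use different counts while SAP 8.2 reports no change. For hormones, the reference for later change is undefined, and change from the first pre-dose value stops at the exposure-1 Day 90 visit.

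**What to change.** - **SAP 7.8:** present relief and rescue by treated-attack number, as in Protocol 10.3, and note where Protocol 10.7 and 10.8 use exposure number. Add a same-subject descriptive display, one row per subject plus totals, for subjects with two or more treated attacks.
- **SAP 7.9:** add a same-subject display of AEs and injection site reactions by exposure, for subjects with exposures 1 and 2 and for those with exposures 1 to 3.
- **SAP 7.9.7:** state the reference value for hormone change at exposures 2 and 3. Beside the per-exposure change, add change from the pre-exposure-1 value to Day 8 and Day 90 after the last dose.
- **SAP 8.2:** record the grouping chosen for efficacy.

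The cost is a few extra descriptive tables from data already collected. Numbers will be small: about 10 for safety and possibly fewer for efficacy, partly because the investigator score is collected only when the subject is treated at the site. These displays remove the composition effect only. Pubertal maturation, menstrual phase, and change of rater or setting remain and should be stated as limits, since there is no control arm.
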